3. EQ-5D-5L

The EQ-5D-5L assesses five dimensions of health (individual health states)⁴: mobility, self-care, usual activities, pain/discomfort, and anxiety/depression. Each dimension has five levels of perceived problems, ranging from no problems to extreme problems.

LEVEL 1: indicating no problem

LEVEL 2: indicating slight problems

LEVEL 3: indicating moderate problems

LEVEL 4: indicating severe problems

LEVEL 5: indicating unable to/extreme problems

Overall QoL utility scores will be derived for all contributing study participants' quality of life assessments using the UK National Institute for Health and Care Excellence (NICE) decision support unit EQ-5D scoring algorithm⁵. This estimation algorithm will directly map from individual-specific, EQ-5D-5L, health states to individual-specific, EQ-5D-3L, utility scores, using age and gender as necessary covariates⁵ to derive utility scores used as the outcome in analyses. The Stata implementation eq5dmap of this algorithm will be used.

The overall score of the EQ-5D-3L index ranges from -0.594 to 1.000. A score of -0.594 represents the worst possible health status while a score of 1.000 represents the best possible health status. A score of 0.000 indicates a health status that is considered as bad as being dead (in terms of quality of life). The absolute minimum score of -0.594 indicates that an individual's health status is worse than being dead because an individual of such health status is not only

experiencing significant health problems but is also experiencing a lower quality of life compared to someone who is deceased. Due to the mapping from 5L to 3L the boundary values cannot be reached and the actual range of possible values is slightly smaller.

The EQ-VAS is a patient-reported measure of perceived overall health. It is a continuous measure that ranges from 0-100, with 100 indicating “the best health imaginable” and 0 indicating “the worst health imaginable.” This score requires no further derivation.

Appendix 3: Dummy tables

Table 1: Baseline demographic and clinical characteristics

	Summary measure	
	Intervention (n=)	Control (n=)
Age – mean (SD) median (IQR)		
Gender, n (%)		
Male		
Female		
Prefer to self-describe		
Missing		
Ethnicity, n (%)		
White British		
White Irish		
White Other		
White and Black Caribbean		
White and Black African		
White and Asian		
Other Mixed Background		
Indian		
Bangladeshi		
Pakistani		
Other Asian Background		
Caribbean		
African		
Black Other		
Chinese		
Other		
Prefer Not To Say		
Missing		
Duration of pain – mean (SD) median (IQR)		
Missing		
Smoking history, n (%)		
Yes		
No		
Missing		
Current smoker, n (%)		
Yes		
No		
Missing		
Average number of cigarettes smoked a day, mean (SD) median (IQR)		
Missing		
Former smoker, n (%)		
Yes		
No		
Missing		

Years last smoked, mean (SD) median (IQR)		
Missing		
Does the participant drink, n (%)		
Yes		
No		
Prefer not to say		
Missing		
Units of wine per week, mean (SD) median (IQR)		
Missing		
Units of beer per week, mean (SD) median (IQR)		
Missing		
Units of spirit per week, mean (SD) median (IQR)		
Missing		

Table 2: Feasibility outcome - concordance in baseline variables between CRF-collected and routinely-collected data

	No. of participants with linked data (N=)	No. of participants with inconsistent linked data (N=)
Age (%)		
Gender (%)		
Ethnicity (%)		
Duration of pain (%)		
Smoking history (%)		
Current smoker (%)		
Average number of cigarettes smoked a day (%)		
Former smoker (%)		
Years last smoked (%)		
Does the participant drink, n (%)		
Units of wine per week (%)		
Units of beer per week (%)		
Units of spirit per week (%)		

Table 3: Feasibility outcomes – recruitment and adherence

Recruitment by MSK Hub	
Tower Hamlets	
No. eligible (N)	
Length of recruitment period (months)	
Rate of eligible patients being presented to hub (N/months)	
No. eligible clinicians willing to recruit (n/N (%))	
No. randomised (n/N(%))	
Newham	
No. eligible (N)	
Length of recruitment period (months)	
Rate of eligible patients being presented to hub (N/months)	
No. eligible clinicians willing to recruit (n/N (%))	
No. randomised (n/N(%))	
Waltham Forest	
No. eligible (N)	
Length of recruitment period (months)	
Rate of eligible patients being presented to hub (N/months)	
No. eligible clinicians willing to recruit (n/N (%))	
No. randomised (n/N(%))	
Cambridge/Norfolk	
No. eligible (N)	
Length of recruitment period (months)	
Rate of eligible patients being presented to hub (N/months)	
No. eligible clinicians willing to recruit (n/N (%))	
No. randomised (n/N(%))	
Overall	
No. eligible (N)	
Length of recruitment period (months)	
Rate of eligible patients being presented to hub (N/months)	
No. eligible clinicians willing to recruit (n/N (%))	
No. randomised (n/N(%))	
Participant adherence	
No. of participants receiving injection (n/ no. randomised (%))	

Table 4: Feasibility outcomes – retention overall and by treatment groups

	Intervention	Control	Overall
General retention			
At 6 Weeks Visit (n/ no. randomised (%))			
At 12 Weeks Visit (n/ no. randomised (%))			
At 26 Weeks Visit (n/ no. randomised (%))			

Table 5: Baseline health economics outcomes – retrospective EQ-5D-5L, EQ-5D-5L at baseline visit

	Intervention (N=)	Control (N=)
Quality of life (EQ-5D-5L) before frozen shoulder		
Mobility, n (%)		
1 no problems		
2 slight problems		
3 moderate problems		
4 severe problems		
5 extreme problems		
Missing		
Self-care, n (%)		
1 no problems		
2 slight problems		
3 moderate problems		
4 severe problems		
5 extreme problems		
Missing		
Usual activities, n (%)		
1 no problems		
2 slight problems		
3 moderate problems		
4 severe problems		
5 extreme problems		
Missing		
Pain/Discomfort, n (%)		
1 no problems		
2 slight problems		
3 moderate problems		
4 severe problems		
5 extreme problems		
Missing		
Anxiety/Depression, n (%)		
1 no problems		
2 slight problems		
3 moderate problems		
4 severe problems		
5 extreme problems		
Missing		
EQ-5D-5L VAS, mean (SD) median (IQR)		
Missing		
EQ-5D-5L Index, mean (SD) median (IQR)		
Missing		
Quality of life (EQ-5D-5L) at baseline		
Mobility, n (%)		

1 no problems		
2 slight problems		
3 moderate problems		
4 severe problems		
5 extreme problems		
Missing		
Self-care, n (%)		
1 no problems		
2 slight problems		
3 moderate problems		
4 severe problems		
5 extreme problems		
Missing		
Usual activities, n (%)		
1 no problems		
2 slight problems		
3 moderate problems		
4 severe problems		
5 extreme problems		
Missing		
Pain/Discomfort, n (%)		
1 no problems		
2 slight problems		
3 moderate problems		
4 severe problems		
5 extreme problems		
Missing		
Anxiety/Depression, n (%)		
1 no problems		
2 slight problems		
3 moderate problems		
4 severe problems		
5 extreme problems		
Missing		
EQ-5D-5L VAS, mean (SD)		
median (IQR)		
Missing		
EQ-5D-5L Index, mean (SD)		
median (IQR)		
Missing		

Table 6: Baseline range of motion measurement

	Intervention (N=)	Control (N=)
Range of motion measurement – researcher		
Method of measurement		
Goniometer (n/N %)		
Photograph Estimation (n/N%)		
Missing (n/N%)		
Frozen shoulder		
Right (n/N %)		
Left (n/N %)		
Missing (n/N %)		
Right shoulder ROM		
Flexion, mean (SD) median (IQR)		
Missing (n/N %)		
External Rotation, mean (SD) median (IQR)		
Missing (n/N %)		
Left shoulder ROM		
Flexion, mean (SD) median (IQR)		
Missing (n/N %)		
External Rotation, mean (SD) median (IQR)		
Missing (n/N %)		
Range of motion measurement – participant		
Method of measurement		
Goniometer (n/N %)		
Photograph Estimation (n/N%)		
Missing (n/N%)		
Frozen shoulder		
Right (n/N %)		
Left (n/N %)		
Missing (n/N %)		
Right shoulder ROM		
Flexion, mean (SD) median (IQR)		
Missing (n/N %)		
External Rotation, mean (SD) median (IQR)		
Missing (n/N %)		
Left shoulder ROM		
Flexion, mean (SD) median (IQR)		
Missing (n/N %)		

External Rotation, mean (SD) median (IQR)		
Missing (n/N %)		

Table 7: Visit 3 health economics outcomes – EQ-5D-5L

	Intervention (N=)	Control (N=)
Quality of life (EQ-5D-5L)		
Mobility, n (%)		
1 no problems		
2 slight problems		
3 moderate problems		
4 severe problems		
5 extreme problems		
Missing		
Self-care, n (%)		
1 no problems		
2 slight problems		
3 moderate problems		
4 severe problems		
5 extreme problems		
Missing		
Usual activities, n (%)		
1 no problems		
2 slight problems		
3 moderate problems		
4 severe problems		
5 extreme problems		
Missing		
Pain/Discomfort, n (%)		
1 no problems		
2 slight problems		
3 moderate problems		
4 severe problems		
5 extreme problems		
Missing		
Anxiety/Depression, n (%)		
1 no problems		
2 slight problems		
3 moderate problems		
4 severe problems		
5 extreme problems		
Missing		
EQ-5D-5L VAS, mean (SD) median (IQR)		
Missing		
EQ-5D-5L Index, mean (SD) median (IQR)		
Missing		

Table 8: Visit 3 range of motion measurement

	Intervention (N=)	Control (N=)
Range of motion measurement – researcher		
Method of measurement		
Goniometer (n/N %)		
Photograph Estimation (n/N%)		
Missing (n/N%)		
Frozen shoulder		
Right (n/N %)		
Left (n/N %)		
Missing (n/N %)		
Right shoulder ROM		
Flexion, mean (SD) median (IQR)		
Missing (n/N %)		
External Rotation, mean (SD) median (IQR)		
Missing (n/N %)		
Left shoulder ROM		
Flexion, mean (SD) median (IQR)		
Missing (n/N %)		
External Rotation, mean (SD) median (IQR)		
Missing (n/N %)		
Range of motion measurement – participant		
Method of measurement		
Goniometer (n/N %)		
Photograph Estimation (n/N%)		
Missing (n/N%)		
Frozen shoulder		
Right (n/N %)		
Left (n/N %)		
Missing (n/N %)		
Right shoulder ROM		
Flexion, mean (SD) median (IQR)		
Missing (n/N %)		
External Rotation, mean (SD) median (IQR)		
Missing (n/N %)		
Left shoulder ROM		
Flexion, mean (SD) median (IQR)		
Missing (n/N %)		

External Rotation, mean (SD) median (IQR)		
Missing (n/N %)		

Table 9: Visit 4 health economics outcomes – EQ-5D-5L

	Intervention (N=)	Control (N=)
Quality of life (EQ-5D-5L)		
Mobility, n (%)		
1 no problems		
2 slight problems		
3 moderate problems		
4 severe problems		
5 extreme problems		
Missing		
Self-care, n (%)		
1 no problems		
2 slight problems		
3 moderate problems		
4 severe problems		
5 extreme problems		
Missing		
Usual activities, n (%)		
1 no problems		
2 slight problems		
3 moderate problems		
4 severe problems		
5 extreme problems		
Missing		
Pain/Discomfort, n (%)		
1 no problems		
2 slight problems		
3 moderate problems		
4 severe problems		
5 extreme problems		
Missing		
Anxiety/Depression, n (%)		
1 no problems		
2 slight problems		
3 moderate problems		
4 severe problems		
5 extreme problems		
Missing		
EQ-5D-5L VAS, mean (SD) median (IQR)		
Missing		
EQ-5D-5L Index, mean (SD) median (IQR)		
Missing		

Table 10: Visit 4 range of motion measurement

	Intervention (N=)	Control (N=)
Range of motion measurement – researcher		
Method of measurement		
Goniometer (n/N %)		
Photograph Estimation (n/N%)		
Missing (n/N%)		
Frozen shoulder		
Right (n/N %)		
Left (n/N %)		
Missing (n/N %)		
Right shoulder ROM		
Flexion, mean (SD) median (IQR)		
Missing (n/N %)		
External Rotation, mean (SD) median (IQR)		
Missing (n/N %)		
Left shoulder ROM		
Flexion, mean (SD) median (IQR)		
Missing (n/N %)		
External Rotation, mean (SD) median (IQR)		
Missing (n/N %)		
Range of motion measurement – participant		
Method of measurement		
Goniometer (n/N %)		
Photograph Estimation (n/N%)		
Missing (n/N%)		
Frozen shoulder		
Right (n/N %)		
Left (n/N %)		
Missing (n/N %)		
Right shoulder ROM		
Flexion, mean (SD) median (IQR)		
Missing (n/N %)		
External Rotation, mean (SD) median (IQR)		
Missing (n/N %)		
Left shoulder ROM		
Flexion, mean (SD) median (IQR)		
Missing (n/N %)		

External Rotation, mean (SD) median (IQR)		
Missing (n/N %)		

Table 11: Visit 5 health economics outcomes –EQ-5D-5L

	Intervention (N=)	Control (N=)
Quality of life (EQ-5D-5L)		
Mobility, n (%)		
1 no problems		
2 slight problems		
3 moderate problems		
4 severe problems		
5 extreme problems		
Missing		
Self-care, n (%)		
1 no problems		
2 slight problems		
3 moderate problems		
4 severe problems		
5 extreme problems		
Missing		
Usual activities, n (%)		
1 no problems		
2 slight problems		
3 moderate problems		
4 severe problems		
5 extreme problems		
Missing		
Pain/Discomfort, n (%)		
1 no problems		
2 slight problems		
3 moderate problems		
4 severe problems		
5 extreme problems		
Missing		
Anxiety/Depression, n (%)		
1 no problems		
2 slight problems		
3 moderate problems		
4 severe problems		
5 extreme problems		
Missing		
EQ-5D-5L VAS, mean (SD) median (IQR)		
Missing		
EQ-5D-5L Index, mean (SD) median (IQR)		
Missing		

Table 12: Visit 5 range of motion measurement

	Intervention (N=)	Control (N=)
Range of motion measurement – researcher		
Method of measurement		
Goniometer (n/N %)		
Photograph Estimation (n/N%)		
Missing (n/N%)		
Frozen shoulder		
Right (n/N %)		
Left (n/N %)		
Missing (n/N %)		
Right shoulder ROM		
Flexion, mean (SD) median (IQR)		
Missing (n/N %)		
External Rotation, mean (SD) median (IQR)		
Missing (n/N %)		
Left shoulder ROM		
Flexion, mean (SD) median (IQR)		
Missing (n/N %)		
External Rotation, mean (SD) median (IQR)		
Missing (n/N %)		
Range of motion measurement – participant		
Method of measurement		
Goniometer (n/N %)		
Photograph Estimation (n/N%)		
Missing (n/N%)		
Frozen shoulder		
Right (n/N %)		
Left (n/N %)		
Missing (n/N %)		
Right shoulder ROM		
Flexion, mean (SD) median (IQR)		
Missing (n/N %)		
External Rotation, mean (SD) median (IQR)		
Missing (n/N %)		
Left shoulder ROM		
Flexion, mean (SD) median (IQR)		
Missing (n/N %)		

External Rotation, mean (SD) median (IQR)		
Missing (n/N %)		

Table 13: Descriptive summary statistics for OSS

OSS	Intervention (N=)				Control (N=)			
	Baseline	V3	V4	V5	Baseline	V3	V4	V5
Complete case analysis (CCA) – n/N (%)								
Mean (SD)								
Median (IQR)								
Missing – n/N (%)								
Participants with no more than 2 items missing – n/N (%)								
Mean (SD) – single imputation (SI)								
Mean (SD) – multiple imputation (MI)								
Median (IQR) – SI								
Median (IQR) – MI								
Missing – n/N (%)								
Participants with at least 1 item completed (retention) – n/N (%)								
Mean (SD) – single imputation (SI)								
Mean (SD) – multiple imputation (MI)								
Median (IQR) – SI								
Median (IQR) – MI								
Missing – n/N (%)								

Table 14 Adjusted treatment effects on OSS, EQ-5D-3L summary index, and ROM at post-randomisation time points if full trial is deemed infeasible.

	V3 (N=)	V4 (N=)	V5 (N=)
OSS			
Treatment - n/N (%)			
Control – n/N(%)			
Adjusted difference in mean OSS between treatment groups* - 95% confidence interval (CI)			
p-value			
EQ-5D-3L Summary Index			
Treatment - n/N (%)			
Control – n/N (%)			
Adjusted difference in mean EQ-5D-3L summary index between treatment groups* - 95% confidence interval (CI)			
p-value			
ROM			
Treatment - n/N (%)			
Control – n/N (%)			
Adjusted difference in mean ROM between treatment groups* - 95% confidence interval (CI)			
p-value			

*Direction of difference: treatment group mean – control group mean. Difference is adjusted for fixed effects (site, age, gender, baseline OSS) and interaction effects between baseline measurements and visits.

Table 15: Total number of AEs by treatment groups and overall

	Intervention (N=)	Control (N=)	Overall (N=)
Overall			
Complications/Expected AE			
Pain at injection site			
Cutaneous infection at injection site			
Loss of subcutaneous fat at injection site causing a skin dimple.			
Steroid flare (transient significant increase of pain symptoms lasting usually no more than 72 hours)			
Disturbance of menstrual cycle			
Transient weakness in arm muscles caused by local anaesthetic leaking around nerves and having a temporary numbing effect lasting no more than a couple of hours			
Significant disturbance in blood sugar level in diabetic patients due to administration of corticosteroid			
Development of septic arthritis due to the introduction of infection to the shoulder joint following injection			
Unexpected AE			

Table 16: Number and proportion of patients with at least 1 AE overall and in each treatment group by study visits

	Intervention (N=)	Control (N=)	Overall (N=)
Overall			
Injection visit			
V3			
V4			
V5			

Table 17: Total number of SAEs by treatment groups and overall

	Intervention (N=)	Control (N=)	Overall (N=)
Overall			
Death			
Life-threatening			
Requires in patient hospitalisation or prolongation of hospitalisation			
Results in significant disability or incapacity			
Congenital anomaly or birth defect			
Requires intervention to prevent permanent impairment			
Deemed by the PI to be medically significant			
Other important medical event			

Table 18: Number and proportion of patients with at least 1 SAE overall and in each treatment group by study visits

	Intervention (N=)	Control (N=)	Overall (N=)
Overall			
Injection visit			
V3			
V4			
V5			

Table 19: Reasons for withdrawal overall and by treatment group

	Intervention (N=)	Control (N=)	Overall (N=)
Overall			
Withdrawal by PI			
Adverse event related			
Withdrawal by patient			
Withdrawal by patient for intervention only (data will be collected up to date of withdrawal)			
Withdrawal by patient for whole study			

Table 20: Number and proportion of withdrawals overall and by treatment group at each time point

	Intervention (N=)	Control (N=)	Overall (N=)
Overall			
V1/Baseline			
V2/ Injection Visit			
V3			
V4			
V5			

Table 21: Number and types of deviations overall and by site

	Tower Hamlets	Newham	Waltham Forest	Cambridgeshire and Peterborough	Overall
Overall					
Data deviation					
Deviation in consent					
Randomisation deviation					
Intervention deviation					
Follow-up deviation					
Others					

Table 22: Number and types of deviations overall and by treatment groups

	Intervention	Control	Overall
Overall			
Data deviation			
Deviation in consent			
Randomisation deviation			
Intervention deviation			
Follow-up deviation			
Others			

Table 23: Participant experience questionnaire overall and by treatment groups

	Intervention (N=) – n/N (%)	Control (N=) – n/N (%)	Overall (N=) – n/N (%)
Participation Questionnaire			
The participant information sheet was easy to understand			
Strongly Agree			

Agree			
Neutral			
Disagree			
Strongly Disagree			
Missing			
Education information/booklet about managing frozen shoulder was easy to understand			
Strongly Agree			
Agree			
Neutral			
Disagree			
Strongly Disagree			
Missing			
Education about managing frozen shoulder was helpful in my recovery			
Strongly Agree			
Agree			
Neutral			
Disagree			
Strongly Disagree			
Missing			
The process of speaking with the research team about the study before I joined was helpful			
Strongly Agree			
Agree			
Neutral			
Disagree			
Strongly Disagree			
Missing			
The consent process was easy to understand and complete			
Strongly Agree			
Agree			
Neutral			
Disagree			
Strongly Disagree			
Missing			
I enjoyed participating in the study			
Strongly Agree			
Agree			
Neutral			
Disagree			

Strongly Disagree			
Missing			
I would participate in another research study in the future			
Strongly Agree			
Agree			
Neutral			
Disagree			
Strongly Disagree			
Missing			
Experience on attending study visits			
Visit1 - Baseline			
Face-to-face			
Phone			
Remote			
SMS			
Email			
Missing			
Visit3 - 6-Week Follow-up			
Face-to-face			
Phone			
Remote			
SMS			
Email			
Missing			
Visit4 - 12-Week Follow-up			
Face-to-face			
Phone			
Remote			
SMS			
Email			
Missing			
Visit5 - 6-Month Follow-up			
Face-to-face			
Phone			
Remote			
SMS			
Email			
Missing			
Order of preference for follow-up session (1= most preferable, 4=least preferable)			
Face-to-face			
1			
2			
3			

4			
Phone			
1			
2			
3			
4			
Remote			
1			
2			
3			
4			
SMS/Email			
1			
2			
3			
4			
Missing			
Outcome measures			
The questions on the measure about how you use your shoulder/arm for everyday activities were relevant			
Strongly Agree			
Agree			
Neutral			
Disagree			
Strongly Disagree			
Missing			
The activities asked about on the measure about how you use your shoulder/arm for everyday activities were important to me			
Strongly Agree			
Agree			
Neutral			
Disagree			
Strongly Disagree			
Missing			
The questionnaire about how I use my shoulder/arm for everyday activities was easy to complete			
Strongly Agree			
Agree			
Neutral			
Disagree			
Strongly Disagree			

Missing			
The questions about my quality of life (if I have problems doing things) were relevant			
Strongly Agree			
Agree			
Neutral			
Disagree			
Strongly Disagree			
Missing			
The activities asked about on the measure my quality of life (If you have problems doing things) were important to me			
Strongly Agree			
Agree			
Neutral			
Disagree			
Strongly Disagree			
Missing			
The questionnaire about my quality of life (if you have problems doing things) shoulder for everyday activities was easy to complete			
Strongly Agree			
Agree			
Neutral			
Disagree			
Strongly Disagree			
Missing

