1.8 Abbreviations

SHEAP	Statistical and Health Economics Analysis Plan
MSK	Musculoskeletal
CCG	Clinical Commissioning Group
CSI	Corticosteroid Injection
CSI & HD	Corticosteroid injection with hydrodilatation
OSS	Oxford Shoulder Score
EQ-5D-5L	European Quality of Life 5 Dimensions 5 Level Instrument
EQ-5D-3L	European Quality of Life 5 Dimensions 3 Level Instrument
ROM	Range of motion
SD	Standard Deviation
IQR	Interquartile Range
AE	Adverse Event
SAE	Serious Adverse Event
IE	Intercurrent Event
CCA	Complete case analysis
SI	Single imputation
MI	Multiple imputation
CI	Confidence interval
AUC	Area under the curve

2. Background and trial design

Study objectives	
To determine the feasibility of an adequately powered definitive trial we will assess:
 
 • The rate of eligible participants presenting to the MSK hubs. • The proportion of eligible participants that clinicians are willing to recruit. • The proportion of eligible participants that are randomised. • Adherence to the study protocol and retention at 6 months. • Data completeness using traditional clinical reporting forms and routine data sources. • Data concordance between traditional clinical reporting forms and routine data sources • Estimand for a definitive trial
Study design	Primary research – Multi-centre, individually-randomised controlled feasibility interventional trial
Setting	
A total of four Musculoskeletal (MSK) Hubs: Three located within Tower Hamlets, Newham and Waltham Forest (TNW) collaborative of Clinical Commissioning Group (CCG). One in Norfolk (East Coast Community Care C.I.C and James Paget Hospitals NHS Foundation Trust).

Participants	
Inclusion Criteria:
 
 • Adults with frozen shoulder • Aged 18 years and older • Loss of passive external rotation of at least 50% compared with the contralateral side • Plain radiographs demonstrating the absence of glenohumeral osteoarthritis or other pathology 
Exclusion Criteria:
 
 • Recurrent ipsilateral frozen shoulder • Presentation following breast cancer or local radiotherapy • Known Rotator cuff tear • Long term systemic corticosteroid use or previous ipsilateral shoulder injection within 12 months

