Health-related quality of life will be assessed using the EuroQol 5 dimensions instrument (EQ-5D-5L)⁴; a valid measure of health-related quality-of-life, consisting of a five-dimension health status classification system (where the lowest level of severity is coded 1 and the highest 5) and a separate visual analogue scale ranging from 0 to 100, with 100 indicating “the best health you can imagine” and 0 indicating “the worst health you can imagine.” VAS score shows the patient’s perceived overall health and requires no further derivation.

Overall QoL utility scores will be derived for all contributing study participants’ quality of life assessments using the UK National Institute for Health and Care Excellence (NICE) decision support unit EQ-5D scoring algorithm⁵. The estimation algorithm will directly map from individual-specific, EQ-5D-5L, health states to individual-specific, EQ-5D-3L, utility scores, using age and gender as necessary covariates⁵. The Stata command eq5dmap will be used to derive the utility scores. Estimated, individual-specific, EQ-5D-3L utility scores will be used as the outcome during statistical analysis. The overall score of the EQ-5D-3L index ranges from -0.594 to 1.000 (i.e., higher scores correspond to a better quality of life).

Upper limb range of motion: forward flexion

Active range of forward flexion is measured between 0-180 degrees, where higher degrees indicate higher mobility of the joint.

The participant will use self-reported charts to self-measure their active range of forward flexion. Research team will also be asked to estimate the participant’s specific range of motion using photographs provided by the participant.

Written instructions and images of how to complete the motion of forward flexion will be provided to the participant. The individual will move their limb into the desired location for measurement and take a photograph. The photograph will be emailed to the research team which will estimate their ROM. This method will allow for collection of data where follow-ups are conducted remotely and telephone if required. The method of participants self-reporting ROM on a chart is currently employed for data collection within the PROFHER-2 Trial (HTA 16/73/03). This will be validated against their OSS score and where patients are reviewed in the MSK hub as part of the routine care with clinician measures of ROM.

Upper limb range of motion: external rotation

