4.1 Sample size calculation

There is no agreed procedure for estimating appropriate sample sizes in feasibility studies. Guidelines suggest recruiting 50-70 participants.^{6,7} Correspondingly, we have selected a convenience sample of 66 participants to determine our ACCORD Protocol version 3.0, 18 November 2022 Page 23 of 32 feasibility objectives. The 95% confidence interval (CI) for a rate estimated to answer a feasibility objective would be at most +/-12.2% wide with a sample size of n=66.

We expect 10 people per month to be diagnosed with frozen shoulder in each MSK Hub. If 25% of these are ineligible and half of the remaining consent to participate in the study, we expect to be able to recruit 2-4 participants per month per site and therefore the convenience sample of 66 participants within 6 months. If these rates were confirmed, we would be able to recruit the required definitive trial sample (anticipated number including attrition=448) within approximately 14 months from 8 Hubs, based upon a recruitment rate of 4 per centre per month and an attrition estimate of 15%.

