4.2 Randomisation procedure

Randomisation will only occur when the research team confirms eligibility, and the participant has provided written, informed consent.

Participants will be randomised in a 1:1:1:1 ratio, stratified by recruiting centre, to one of the following:

- CSI&HD and patient to self-measure ROM self-measured before 6 week (+/- 3 days) visit
- CSI&HD and patient to self-measure ROM self-measured after 6 week (+/- 3 days) visit
- CSI alone and patient to self-measure ROM self-measured before 6 week (+/- 3 days) visit
- CSI alone and patient to self-measure ROM self-measured after 6 week (+/- 3 days) visit

The allocation will be determined just prior to the time of the injection, using a web-based, distant randomisation service administered by the Pragmatic Clinical Trials Unit, QMUL. Allocation lists using random permuted blocks of sizes 4 and 8 will be prepared by the trial statistician with the final lists being uploaded to the randomisation system by an independent statistician.

The clinician providing the injection will contact a member of the research team once the participant has arrived for their appointment. The research team member who is appropriately and sufficiently trained and delegated to complete randomisation will randomise the patient and communicate the allocation to the treating clinician.

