5.3 Analysis of clinical and health economics outcomes

Descriptive statistics will be used to summarise all clinical and health economics outcome measures at each time point in each group.

As this is a feasibility study and the sample size is small, there will be no significance testing, except for circumstances described in 5.3.1, where the definitive trial is deemed infeasible.

Complete case analyses are assumed unless otherwise specified.

For Oxford Shoulder Score (OSS):

- Mean (SD) and median (IQR) will be presented for each group at each time point
- Sensitivity analyses will be conducted on mean (SD) and median (IQR) by presenting and comparing statistics derived using different methods of imputation on individual missing items (see 5.6 for more details)
- Percentage of missing will be presented for each group at each time point

For range of motion (ROM) – forward flexion:

- Mean (SD) and median (IQR) will be presented for each group at each time point
- Percentage of missing will be presented for each group at each time point

For range of motion (ROM) – external rotation:

- Mean (SD) and median (IQR) will be presented for each group at each time point
- Percentage of missing will be presented for each group at each time point

For each domain of health-related quality of life (EQ-5D-5L):

- Proportion of participants at each level
- Percentage of missing will be presented for each group at each time point

For health-related quality of life (EQ-5D-5L) summary index:

- Mean (SD) and median (IQR) will be presented for each group at each time point
- If the score for a domain is missing, then the overall index would be treated as missing
- Percentage of missing will be presented for each group at each time point

For health-related quality of life (EQ-5D-5L) VAS score:

- Mean (SD) and median (IQR) will be presented for each group at each time point
- Percentage of missing will be presented for each group at each time point

For cost of resources used (2023£): healthcare costs, personal care costs, time-off-work costs, out-of-pocket costs

- Mean (SD) and median (IQR) will be presented for each group at each time point

- Percentage of missing will be presented for each group at each time point

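### The descriptive ROM tables are laid out by right and left shoulder, so no row shows the mean or SD for the frozen shoulder

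*SAP*

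**What the plan says.** Appendix 3 of the SAP has one ROM table per measurement visit: Table 6 (baseline), Table 8 (Visit 3), Table 10 (Visit 4) and Table 12 (Visit 5). Each has a researcher block and a participant block. Within a block, the side of the frozen shoulder is a count (right, left, missing). Mean (SD) and median (IQR) of flexion and external rotation then follow under "Right shoulder ROM" and "Left shoulder ROM", by arm. Side is not crossed with ROM.

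The text of the SAP does not say which shoulder is the outcome:

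- Section 3.2 defines the measure by movement and scale only: "Active range of forward flexion is measured between 0-180 degrees, where higher degrees indicate higher mobility of the joint". External rotation is handled in the same way.
- Section 5.3 promises, for each movement, "Mean (SD) and median (IQR) will be presented for each group at each time point". That is one summary, not one per side.
- Section 5.3.1 says that ROM will use the same model as the Oxford Shoulder Score (OSS), or an equivalent. Table 14 reports a single "Adjusted difference in mean ROM between treatment groups" at each follow-up visit. Neither names a shoulder.
- Appendix 2, which derives the outcomes, has no entry for ROM.

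**The concern.** The two shoulders of a participant differ by design. Section 2 makes it an entry condition that there is "Loss of passive external rotation of at least 50% compared with the contralateral side". A row that pools right shoulders across an arm therefore pools frozen shoulders (right-sided cases) with the other shoulder of left-sided cases. Its mean describes neither kind, and its SD contains the gap between them.

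Section 3.2 lists ROM among the outcomes proposed for a full trial. To judge it for that use, a reader needs its level, spread and change in the frozen shoulder, by arm and visit. The planned tables do not provide these.

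**Working it through.** The SAP gives no expected ROM values, SD or effect, so there is no planned figure to reproduce. The layout is read from the tables; its consequence is illustrated with assumed values.

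**Inputs from the SAP**
- Section 4.1: "we have selected a convenience sample of 66 participants". Pooling the two ROM-timing cells within each treatment gives 66/2 = 33 per arm.
- Section 4.2: "Participants will be randomised in a 1:1:1:1 ratio, stratified by recruiting centre, to one of the following". Affected side is not a stratum, so it can differ between arms by chance.

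**Assumed inputs (not in the SAP)**
- p, the share of an arm whose right shoulder is frozen: 0.3 to 0.7.
- External rotation: unaffected mean H = 60 degrees, frozen mean F = 30 (a 50% loss), SD within each kind of shoulder s = 15.
- Flexion: H = 160, F = 90, s = 20.
- D, the treatment effect on the frozen shoulder: 10 degrees.

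**Formulas**
- Right-row mean = pF + (1 − p)H; left-row mean = (1 − p)F + pH.
- Row SD = sqrt(s² + p(1 − p)(H − F)²).
- Effect shown, if p is equal in both arms: pD in the right row and (1 − p)D in the left row.
- SE of the arm difference in a row caused only by chance imbalance of side: (H − F) × sqrt(2p(1 − p)/33).

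**Means.** For external rotation at p = 0.5, both rows show 0.5 × 30 + 0.5 × 60 = 45, while the frozen mean is 30. At p = 0.3 the right row shows 51 and the left 39; at p = 0.7 these reverse.

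**SD at p = 0.5**
- External rotation: sqrt(225 + 0.25 × 900) = sqrt(450) = 21.2, against 15.
- Flexion: sqrt(400 + 0.25 × 4900) = sqrt(1625) = 40.3, against 20.
- The result follows the gap. With F = 20 for external rotation it is sqrt(225 + 0.25 × 1600) = 25.0. If recovery narrows the gap to 20 degrees it is sqrt(225 + 0.25 × 400) = 18.0.

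**Effect shown.** At p = 0.5 a 10-degree effect appears as 5 degrees in each row. Over p = 0.3 to 0.7, a row shows 30% to 70% of it.

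**Chance imbalance (external rotation).** At p = 0.5 the SE is 30 × sqrt(0.5/33) = 3.7 degrees; at p = 0.3 or 0.7 it is 30 × sqrt(0.42/33) = 3.4 degrees. The affected-shoulder mean does not carry this component.

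**Can the reader undo the mixing?** Not reliably. Solving the two row means for F and H with the side counts requires assuming that ROM does not depend on which side is frozen. At p = 0.5 the two equations coincide and there is no solution.

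**The case against.** The strongest reply is that mixing is inferred, not stated. The right and left rows come directly after the count of frozen side, so each row might be meant only for participants frozen on that side. The protocol, which was not available for this review, may also say which shoulder counts. This has some force: the SAP is ambiguous, and the restricted reading would remove the mixing. But no such restriction is written. Even with it, the outcome would be spread over two subsets, with no overall affected-shoulder mean or SD, and Section 5.3's single summary would still have no row to fill.

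A reader might also infer four stronger things, which the SAP does not support:

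- *That all planned ROM results are mixed.* Section 5.3 and Table 14 do not split by side. They leave the shoulder undefined, which is a different fault.
- *That the full trial would be sized wrongly.* An SD of 40.3 against 20 would multiply a sample size by about four ((40.3/20)² = 4.06). But Section 6.6 takes its SD from OSS differences, and the alternative in Section 6.1 is an area under the OSS curve. No planned calculation uses a ROM SD.
- *That a treatment comparison loses power.* Section 5.3 rules out testing unless a full trial is judged infeasible. In that case ROM is compared through the Section 5.3.1 model and Table 14, not through the right and left rows.
- *That the agreement analysis in Section 5.2.2 is harmed.* Self-measured and clinician-measured ROM can be compared on either shoulder; restricting that analysis to the affected one is optional.

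Finally, frozen side is recorded, so correct tables can be made from the same data.

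**Conclusion.** The point holds for the descriptive ROM results. Followed as written, Tables 6, 8, 10 and 12 never show ROM of the frozen shoulder, they do not match the single summary promised in Section 5.3, and neither Section 5.3.1 nor Table 14 settles which shoulder is analysed.

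The direction needs few assumptions: if rows pool both kinds of shoulder, any mixed side split dilutes an effect confined to the frozen shoulder, and any gap between shoulders inflates the SD. The size rests wholly on assumed values: about half the effect at an even split, and an SD larger by a factor of about 1.4 (21.2/15) to 2.0 (40.3/20) in the two main scenarios, less where the gap narrows. The damage is limited to describing ROM and judging it as a full-trial outcome. Data collection, randomisation, OSS results and the planned sample size are untouched.

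**What to change.** 1. In Tables 6, 8, 10 and 12, replace the right and left rows by affected-shoulder and contralateral-shoulder rows, in both the researcher and participant blocks. Keep the right/left count of frozen side as a baseline characteristic.
2. State in Sections 3.2, 5.3 and 5.3.1, and in Table 14, that the ROM outcome is that of the affected shoulder.

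The cost is four table shells and one sentence repeated where ROM is defined and analysed. The tables already provide for frozen side and ROM of both shoulders, so no new data are needed. It is best done before results by arm are seen, so that the shoulder is not chosen afterwards.
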